Consensus exists that the phenomenology of post-COVID-19 condition is subserved by disturbance in immune-inflammatory systems⁷. Currently, no treatment is identified as safe and effective for post-COVID-19 condition^{7,8}. A candidate treatment for post-COVID-19 condition should be capable of improving measures of cognitive function (i.e., objective and subjective), motivation and energy, as well as reducing fatigue⁷⁻⁹. The rationale for prioritizing cognition as a primary therapeutic target is based on a concatenation of study results reporting that cognitive complaints/deficits and fatigue are some of the most common and debilitating features of post-COVID-19 condition¹⁰⁻¹². The candidate treatment would be preferred to target biological systems subserving circadian rhythms, as well as reward and reinforcement brain mechanisms. The profile of the candidate treatment should also have preliminary evidence documenting favourable modulatory effects on circulating pro-inflammatory cytokines, as well as immune cellular systems (e.g., macrophages). Preliminary evidence suggests that some antidepressants (e.g., SSRIs) are capable of reducing respiratory complications secondary to COVID-19^{13,14}. Putative mechanisms implicated include sigma-1 agonism and acid sphingomyelinase¹³. A limitation of SSRIs, however, for specifically targeting post-COVID-19 condition, is that they are not proven to be pro-cognitive and/or beneficial for reward systems and are, instead, reported to have, in some cases, dyscognitive and reward blunting effects (e.g., emotional blunting)^{13,15-17}.

Vortioxetine is established as pro-cognitive, as evidenced by significant improvement on both subjective and objective measures^{18,19,20}. Vortioxetine is also documented to improve anticipatory and consummatory measures of reward function/anhedonia as evaluated by validated reward paradigms, as well as the Snaith Hamilton Pleasure Scale (SHAPS)^{21,22}. Vortioxetine also improves general functioning¹⁸. Furthermore, vortioxetine has demonstrated significant improvement on measures of motivation and energy^{23,24}. Moreover, vortioxetine is not associated with emotional blunting and has preliminary evidence of improving sleep behaviour and circadian rhythms^{23,25}. The candidacy of vortioxetine as an effective treatment for post-COVID-19 condition is also strengthened by evidence indicating that vortioxetine exerts modulatory effects on cellular and cytokine systems known to be activated in persons with post-COVID-19 condition^{26,27}.

Hypotheses

Herein, we hypothesize that vortioxetine (5-20 mg) will be more effective than placebo in the treatment of cognitive impairment in persons with post-COVID-19 condition.

Study Design

Eight-week, randomized, double-blinded, placebo-controlled clinical trial

- Eight-week intervention (i.e., weeks 0-8)
- Two-week drug discontinuation and safety follow-up period (i.e., weeks 8-10)

Primary Endpoint: Week 8

Outcomes

Primary Outcomes

- Baseline-to-endpoint (i.e., Week 8) change in Digit Symbol Substitution Test (DSST) (Pen/Paper Version and Online CogState Version as part of the CogState Online Cognitive Battery). Remote participants will not complete the pen/paper version of the DSST.

Secondary Outcomes

- Baseline-to-endpoint change in:
 - CogState Online Cognitive Battery
 - Trails Making Test (TMT)-A/B
 - Rey's auditory verbal learning test (RAVLT)
 - Perceived Deficits Questionnaire, 20-item (PDQ-20)
 - Fatigue Severity Scale (FSS)
 - Snaith Hamilton Pleasure Rating Scale (SHAPS)
 - Generalized Anxiety Scale, 7-item (GAD-7)
 - World Health Organization Wellbeing Scale, 5-item (WHO-5)
 - EuroQol, 5-dimension, 5-level (EQ-5D-5L)
 - Sheehan Disability Scale (SDS)
 - Post-Covid Functional Scale (PCFS)
 - fMRI and the Effort Expenditure for Rewards Task (EEfRT)
 -
 - Behavioural Activation Scale (BAS)
 - International Physical Activity Questionnaire (IPAQ)
 - Quick Inventory of Depressive Symptomatology (16-Item) (Self-Report) (QIDS-SR16)
- Safety outcomes
 - Spontaneously reported adverse events
 - Laboratory (including but not limited to CBC, TSH, electrolytes)

Study Population

Inclusion Criteria

- Age 18+
- Meets WHO-defined post-COVID-19 condition
 - WHO definition: 'Post COVID-19 condition occurs in individuals with a history of probable or confirmed SARS-CoV-2 infection, usually 3 months from the onset of

COVID-19 with symptoms that last for at least 2 months and cannot be explained by an alternative diagnosis. Common symptoms include fatigue, shortness of breath, cognitive dysfunction but also others and generally have an impact on everyday functioning. Symptoms may be new onset following initial recovery from an acute COVID-19 episode or persist from the initial illness. Symptoms may also fluctuate or relapse over time.⁶

- To ensure the above criteria is met, participants will only be included in the study if they meet all eligibility criteria more than 12 weeks from their confirmed and documented positive polymerase chain reaction (PCR) SARS-CoV-2 test, rapid antigen, or antibody test. In lieu of a prior positive test, a signed confirmation of a presumptive prior COVID-19 case from a healthcare provider, including the study physician, is acceptable.
- Documented history of SARS-CoV-2 infection with typical symptoms, and requiring positive SARS-CoV-2 test (PCR, antigen, or serology) at some point during the course of the acute course of illness. In lieu of a prior positive test, a confirmation of a presumptive prior COVID-19 case from a healthcare provider, including the study physician, is acceptable.
- Subjective cognitive complaints as detected by the Perceived Deficits Questionnaire (PDQ)-5.
- Ability to provide written informed consent.
- Resident of Canada.

Exclusion Criteria

- Current symptoms are fully explained by major depressive disorder or bipolar disorder.
- Pre-existing conditions that may cause cognitive impairment, or symptoms similar to those seen in post-COVID-19 condition (e.g., ADHD, major neurocognitive disorder, schizophrenia, chronic fatigue syndrome [CFS]/ encephalitis meningitis [EM]), as assessed by Mini International Neuropsychiatric Interview (MINI) 7.0.2.
- Inability to follow study procedures.
- Known intolerance to vortioxetine and/or prior trial of vortioxetine with demonstrated inefficacy.
- If participants are currently taking other antidepressants, they will be asked to discontinue the antidepressant for 2-4 weeks in order to participate in the study.
- Patients on other antidepressants are allowed to participate only if the antidepressant is prescribed at subtherapeutic doses for a primary indication other than mood disorders. Participants will be made aware in the consent form that the combination of the two antidepressants would be considered investigational and that the safety/efficacy profiles are unknown ²⁸⁻³⁰.
- Current alcohol or substance use disorder.
- Inability to provide consent.
- Current alcohol and/or substance use disorder as confirmed by the M.I.N.I 7.0.2.
- Presence of comorbid psychiatric disorder that is a primary focus of clinical concern as confirmed by the M.I.N.I. 7.0.2.
- Medications approved and/or employed off-label for cognitive dysfunction (e.g., psychostimulants).

- Any medication for a general medical disorder that, in the opinion of the investigator, may affect cognitive function.
- Use of benzodiazepines within 12 hours of cognitive assessments.
- Consumption of alcohol within 8 hours of cognitive assessments.
- Physical, cognitive, or language impairments sufficient to adversely affect data derived from cognitive assessments.
- Diagnosed reading disability or dyslexia.
- Clinically significant learning disorder by history.
- Electroconvulsive therapy (ECT) in the last 6 months.
- History of moderate or severe head trauma (e.g., loss of consciousness for >1 hour), other neurological disorders, or unstable systemic medical diseases that in the opinion of the investigator are likely to affect the central nervous system.
- Pregnant and/or breastfeeding.
- Received investigational agents as part of a separate study within 30 days of the screening visit.
- Actively suicidal/presence of suicidal ideation or evaluated as being at suicide risk (as per clinical judgment).
- Currently receiving treatment with Monoamine Oxidase Inhibitors (MAOIs) antidepressants, antibiotics such as linezolid, or intravenous methylene blue.
- Previous hypersensitivity reaction to vortioxetine or any components of the formulation. Angioedema has been reported in patients treated with vortioxetine.
- Serotonin syndrome.
- Abnormal bleeding.
- Previous history of mania/hypomania.
- Angle closure glaucoma.
- Hyponatremia.
- Moderate hepatic impairment.
- Active seizure disorder/epilepsy, not controlled by medication (per study physician assessment).
- Presence of any unstable medical conditions.

Recruitment

Recruitment will take place via media announcements (e.g., print, social media, public broadcasting stations). Announcement of study recruitment will also be provided to primary health care providers in Canada.

Study Visits

Study visits may be conducted remotely (e.g. zoom), by telephone or in-person. Visits with the study physician will primarily occur via a secure online platform (e.g. OTN) or by telephone. If required/requested, in-person visits with the study physician may be scheduled.

Participants may be emailed a secure, unique and anonymized RedCap link to complete self-report questions at home within 24 hours of their scheduled visit (before or after visit). This is to reduce participant burden during the visit with research staff/study physicians. Participants will

be asked to complete self-report questionnaires at the same time block of the day during all study visits (i.e. all mornings, afternoons or evenings).

Pre-Screen

Participants will be pre-screened via telephone, email, or an online form to determine if they meet above noted inclusion and exclusion criteria.

Screening Visit (Visit 0)

Once participants provide written, informed consent, they will undergo a comprehensive assessment to determine eligibility during the screening visit. Details of assessments completed are included in Table 1.

Baseline (Visit 1)

Participants will undergo the various assessments listed in Table 1. In addition, participants will have their blood drawn and may be invited to participate in an optional fMRI scan (see details below). Participants will also be assessed by a study physician at one time point between the screening and baseline visits and be provided a prescription for vortioxetine. Research staff (i.e. research coordinators/research assistants) will dispense the medication to the participant based on the direction from the study physician/prescription from the study physician for the first two weeks of the study. For remote participants, research staff will mail medication for the first two weeks of the study with appropriate temperature monitoring.

Laboratory Assessment: Participants will be asked to fast for 8 hours prior to their baseline (visit 1) and week 8 (visit 4). Participants will have blood drawn for standard clinical parameters. These include glucose, insulin, electrolytes, liver and kidney function tests, lipids, CBC, inflammatory markers (e.g. CRP, ESR), albumin and protein. Participants may also have their blood drawn for various exploratory secondary analyses (e.g. cytokines). Approximately 20 mL of blood will be drawn in 4-5 blood tubes. Two of these tubes will include lavender tubes with EDTA for exploratory analyses. A urine or blood pregnancy test will be conducted for all female participants.

Remote participants will be provided a blood requisition form via email or mail to have clinical blood drawn and analyzed at the participant's local blood lab facility. Blood will not be collected for exploratory purposes from remote participants. Female participants may provide a blood or urine sample to the local blood lab to confirm non-pregnancy. Participants may also be mailed a home pregnancy test.

Exploratory Blood Analyses: For participants seen in-person, they will be able to volunteer to provide a blood sample for exploratory analyses. The sample will be collected at a local blood lab (e.g. Mount Sinai Hospital), followed by processing and storage of the sample at the Biospecimen Repository and Processing Lab (Lunenfeld-Tanenbaum Research Institute, Sinai Health). Participants may also have blood drawn at the same time for clinical purposes at Mount Sinai Hospital. The clinical blood tubes will be delivered to another local lab (e.g. Dynacare, LifeLabs) for analyses. Alternatively, participants may also have blood drawn separately for clinical analyses at a local blood lab near them - this will result in two separate blood draws.

fMRI: A subset of participants may be offered the opportunity to have an fMRI scan completed at baseline and endpoint for secondary, exploratory purposes. This is optional and not the primary focus of the study. Participants may still participate in the study and decide not to participate in this component. During the imaging, participants will be asked to complete a cognitive task (e.g. Effort Expenditure for Rewards Task, Trails Making Test A/B). Participants will be awarded the amount of money they earn during this task, on top of the standard compensation to all participants. Please see “Participant Compensation” for more details.

Week 2 (Visit 2): Participants will complete items listed in Table 1, Week 2 (Visit 2). The study physician will determine if the participant is eligible for a dose increase. Research staff (i.e. research coordinators/research assistants) will dispense medication to the participant based on the direction from the study physician/prescription from the study physician for the next six weeks of the study. For remote participants, medication for the remaining six weeks of the study will be mailed out as well as medication for discontinuation by research staff with appropriate temperature monitoring.

Week 4 (Visit 3): Participants will complete items listed in Table 1, Week 4 (Visit 3).

Week 8 (Visit 4): Participants will complete items listed in Week 8 (Visit 4). The study physician will also discuss transition of care (see below) and/or medication continuation. Participants will also have their blood drawn and may be asked to participate in the optional fMRI scan.

Optional Post-Study (Week 10): Clinical visit with physician if the participant is discontinuing the study medication and/or as needed. If a participant chooses to continue with the study medication, he/she will be asked to follow up with his/her most responsible physician (MRP) for ongoing care and this post-study visit would not be needed. Participants will be informed prior to signing the consent form that research staff/research physician will not be able to tell them if they received drug or placebo when they finish the study at week 8 and they will have to wait until the entire study is complete to find out.

Table 1. Study schedule with assessments

Study Visit	Screening (Visit 0)	Baseline (Visit 1)	Visit 2	Visit 3	End-of-study (Visit 4)
Week	(-1 to -21 days from baseline)	0	2 (+/- 2 days)	4 (+/- 2 days)	8 (+/- 2 days)
Consent	X				
Inclusion/Exclusion	X				
Demographics	X				
Past COVID-19 Infection Information	X				

M.I.N.I 7.0.2	X				
Psychiatric/Medical History	X				
Lifestyle Factors	X				
Current Medications	X	X	X	X	X
Medication Changes	X	X	X	X	X
Adverse Events		X	X	X	X
Anthropometrics		X	X		X
MoCA		X			
SETS		X			
DSST		X	X		X
TMT-A/B		X	X		X
RAVLT		X	X		X
CogState Online Cognitive Battery**		X	X		X
PDQ-20		X	X	X	X
GAD-7		X	X	X	X
SHAPS		X	X	X	X
FSS		X	X	X	X
WHO-5		X	X	X	X
SDS		X	X	X	X
BAS		X	X	X	X
EQ-5D-5L		X	X	X	X
QIDS-SR16		X	X	X	X
IPAQ		X		X	X
PCFS	X	X	X	X	X
EEfRT		X			X

Physician Assessment*	X		X	X	X
Laboratory assessments		X			X
fMRI + Cognitive Test		X			X

Abbreviations: ^a: BAS: Behavioural Activation Scale; DSST: Digit Symbol Substitution Test; EQ-5D-5L: 5-Level EQ-5D version; fMRI: functional magnetic resonance imaging; FSS: Fatigue Severity Scale; GAD-7: Generalized Anxiety Disorder, 7-item; IPAQ: International Physical Activity Questionnaire; EEfRT: Effort Expenditure for Rewards Task ; M.I.N.I: Mini-International Neuropsychiatric Interview; MoCA: Montreal Cognitive Assessment; PCFS: Post-Covid Functional Scale; PDQ-20: Perceived Deficits Questionnaire, 20-item; Quick Inventory of Depressive Symptomatology (16-Item) (Self-Report) (QIDS-SR16); RAVLT: Rey's auditory verbal learning test; RPE: Borg Rating of Perceived Exertion Scale; SDS: Sheehan Disability Scale; SETS: Stanford Expectations of Treatment Scale; SHAPS: Snaith-Hamilton Pleasure Scale; TMT-A/B: Trails Making Test-A/B; WHO-5: World Health Organization Well-Being Index, 5-item.

*One physician assessment will be conducted between the baseline and screening visit.

**May be conducted remotely.

Sample Size

- Total recruitment N=200 (i.e., 100 subjects allocated to vortioxetine [5-20 mg] and placebo each).
- The target sample size is based on effect sizes reported by previous clinical trials that evaluated the efficacy of antidepressants vs placebo and nutraceuticals in individuals with chronic fatigue syndrome ^{6,23-25}.
- The effect size of vortioxetine on DSST-measured cognitive function is estimated at approximately 0.2-0.5 ^{26,27}. Previous experience without patients enrolled in clinical trials (investigator-initiated trials) with vortioxetine as part of the THINC-it tool validation indicated that vortioxetine improves measures of processing speed (the prominent domain validated by the DSST) of significance with a sample size of 200.
- It is then estimated that a sample size of 100 per treatment arm would detect clinically relevant change with vortioxetine treatment on DSST as the dependent measure ^{27,31}.

Feasibility

- It is estimated, based on prior general population research conducted by the BCDF, that recruitment will take approximately 12 months.
- Community research ethics board approval, 2-4 weeks (BCDF is an independent research center not requiring university- or hospital-based REB reviews).

Description of Study Procedures

Efficacy Assessments

Digit Symbol Substitution Test (DSST)

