- Other tests: Chloride, Bicarbonate, C-reactive peptide (CRP), erythrocyte sedimentation rate (ESR), estimated glomerular filtration rate (eGFR)

- hCG pregnancy screen (as applicable)

A urine pregnancy test will be administered if no hCG pregnancy screen has been conducted.

In the event of an unexplained clinically significant abnormal laboratory test value, the test should be repeated and will be followed up until it has returned to the normal range and/or an adequate explanation of the abnormality is found.

Adverse Events

All AEs occurring after the participant signs the ICF and up to the last study event will be recorded. Any unresolved AEs that are ongoing at the end of the study will be followed until resolution or no longer considered clinically significant by the investigator.

Other Assessment Instruments

Mini International Neuropsychiatric Interview Version 7.0.2 (M.I.N.I. Version 7.0.2)

The MINI was designed as a brief structured interview for the major Axis I psychiatric disorders in DSM-5 and International Classification of Diseases-10. Validation and reliability studies have been done comparing the MINI to the Structured Clinical Interview for DSM-5 Patient Edition and the Composite International Diagnostic Interview (a structured interview developed by the World Health Organization). Version 7.0.2 of the MINI will be used for this study. The results of these studies show that the MINI has similar reliability and validity properties, but can be administered in a much shorter period (mean 18.7 ± 11.6 min, median 15 min) than the above referenced instruments. It can be used by clinicians after a brief training session. At screening, participants will be assessed for MDD and BD, as documented by DSM-5 criteria, and the lack of other psychiatric diagnoses will be confirmed by use of the MINI.

Montreal Cognitive Assessment (MoCA)

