Excipients: Gelatin, Red Iron Oxide, Titanium Dioxide. The filler used for both the active capsule with vortioxetine and the entire placebo capsule is Capsulac® 60 Lactose Monohydrate (Ph.Eur/USP-NF/JP).

Individuals aged 65 may start at 5mg or 10mg on days 1-14, and this dose may be titrated to 10mg or 20mg, respectively, at the start of week 3 based on the recommendation of the study physician.

Side effects

- Serotonin Syndrome has been reported with serotonergic antidepressants (SSRIs, SNRIs, and others), including with vortioxetine both when taken alone, but especially when coadministered with other serotonergic agents (including triptans, tricyclic antidepressants, fentanyl, lithium, tramadol, tryptophan, buspirone, and St. John's Wort).
- Treatment with serotonergic antidepressants (SSRIs, SNRIs, and others) may increase the risk of abnormal bleeding. Patients should be cautioned about the increased risk of bleeding when Vortioxetine is coadministered with nonsteroidal anti-inflammatory drugs (NSAIDs), aspirin, or other drugs that affect coagulation.
- Activation of Mania/Hypomania can occur with antidepressant treatment.
- Angle Closure Glaucoma: Angle closure glaucoma has occurred in patients with untreated anatomically narrow angles treated with antidepressants.
- Hyponatremia can occur in association with the syndrome of inappropriate antidiuretic hormone secretion (SIADH).

Most Common

- Gastrointestinal adverse events; including nausea, vomiting, constipation/diarrhea. Highest incidence occurs during the first week of treatment: 21-32%
- Sexual dysfunction: 14-34%

Less Common: 1-10%

- Dry mouth
- Dyspepsia (discomfort of the abdomen)
- Dizziness
- Somnolence/sedation
- Fatigue
- Insomnia
- Abnormal dreams
- Hyperhidrosis (increase sweating)
- Arthralgia (joint pain)
- Decreased appetite
- Itchy skin
- Nasopharyngitis

Rare: Less than 1%

- Nervous system disorders
- Skin and subcutaneous tissue disorders
- Psychiatric disorders
- Abnormal bleeding

- Clinical worsening or suicide risk

Post-Market Adverse Reactions

The following adverse events have been identified during post-approval use of Vortioxetine. These events are reported voluntarily from a population of uncertain size, and it is not possible to reliably estimate their frequency or establish a causal relationship to drug exposure.

- Hyperprolactinaemia
- Acute pancreatitis
- Anaphylactic reaction
- Serotonin syndrome, headache
- Agitation, aggression
- Angioedema

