Adverse events will be collected from baseline to endpoint. At each visit, subjects will be asked if they have experienced any health problems or side effects since the previous visit. All AEs will be recorded appropriately, whether or not considered related to the investigational product. This will include AEs spontaneously reported by the patient and/or observed by members of the research team as well as AEs reported in response to a direct question (e.g., "Have you experienced any health problems or side-effects since your last visit?").

For each AE, the following parameters will be described:

- Discovery (i.e., spontaneous or solicited)

- Start date
- Stop date or ongoing
- Action taken with regards to investigational product
- Outcome if the AE caused the patient to discontinue the investigational product
- A statement if the AE fulfills the criteria for a SAE or not
- The investigator's assessment of the causal relationship between the event and the investigational product
- Intensity of the AE
 - Mild (awareness of sign or symptom, but easily tolerated)
 - Moderate (discomfort sufficient to cause interference with normal activities)
 - Severe (incapacitating, with inability to perform normal activities)
- Resolution

Assessment of Causality

Each AE will be assessed as to its relationship to the IP, based on the following criteria. Although the attribution by the investigator will be collected for reported events, for analytic purposes a temporal association with the use of the IP will be assumed sufficient for at least plausible association.

- Not related: No causal relationship exists between the IP and the AE, but an obvious alternative cause exists, eg, the participant's underlying medical condition or concomitant therapy.
- Possibly related: A connection with the administration of the IP appears unlikely, but cannot be ruled out with certainty. An AE may be considered possibly related if or when it meets 2 of the following criteria: (1) it follows a reasonable temporal sequence from administration of the IP; (2) it could not readily have been produced by the participant's clinical state, environmental or toxic factors, or other modes of therapy administered to the participant; or (3) it follows a known pattern of response to the IP.
- Related: There is a reasonable/plausible possibility that the AE may have been caused by the IP.

When assessing the relationship to the IP, the following criteria will be considered:

- Known class effect

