- The MMRM model will use study visit as a fixed factor and the interaction between treatment and visit to allow for estimation of treatment effect at specific time points. Additionally, the interaction term of visit and baseline to allow for time dependent adjustment of baseline. An unstructured covariance matrix will be used.

To control for type I error, the following sequence of hierarchically ordered primary and key secondary end points will be used at a significance level of 0.05 1-sided for the primary outcome:

- Primary endpoint: Change from baseline to week 8 between vortioxetine and placebo in DSST performance score
- Secondary endpoint: Change from baseline to week 2 between vortioxetine and placebo in DSST performance score

The change from baseline in DSST performance score after 8 weeks of treatment will be analyzed with a one-sided mixed model for repeated measures (MMRM) with treatment and study visits as fixed factors and baseline DSST performance as covariate. For secondary analyses, the change from baseline in DSST, CogState Online Cognitive Battery, PDQ-20, TMT-A/B, SHAPS, FSS, GAD-7, WHO-5, EQ-5D-5L, BAS, RPE, RAVLT, PCFS, EEfRT, SETS, QIDS-SR16, IPAQ and SDS will also be analyzed using a mixed model for repeated measures (MMRM) using all available data. Withdrawal rates will be compared between placebo- and vortioxetine-randomized participants at week 8.

A power calculation was obtained via computer simulations on the primary outcome of difference in the change from baseline in DSST performance score between vortioxetine and placebo. Assuming an SD of 8.0 for the change from baseline in the DSST performance score

at week 1 and a 15% dropout rate, based on previous randomized, placebo-controlled trials with vortioxetine, it was calculated that 100 subjects (modified per treatment group) are required to achieve 80% power to detect a difference of 3.1 in the change from baseline in DSST performance score between vortioxetine and placebo (i.e., Cohen's $d=0.38$) by an MMRM with a 1-sided significance level of $p<0.05$ ^{26,53}.

The magnitude of fMRI-determined ventral striatal (including nucleus accumbens) activation during anticipation of gain versus no-incentive trials, as well as loss versus no-incentive trials, in the EEfRT task. Mean and maximum fMRI ventral striatal activation will be assessed.

Publication Plan

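### The outcome list and the recording rules disagree on which adverse events form the safety outcome, and the statistical section neither settles this nor plans an adverse-event summary

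*Combined protocol and SAP*

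**What the plan says.** - **Outcomes, Safety outcomes.** Two items are listed. The first is "Spontaneously reported adverse events"; the second is laboratory tests. There is no separate item for serious adverse events or for events that lead to withdrawal.
- **Safety Assessments, Adverse Events.** Recording is not restricted by how an event comes to light: "All AEs occurring after the participant signs the ICF and up to the last study event will be recorded".
- **Recordings of Adverse Events.** "At each visit, subjects will be asked if they have experienced any health problems or side effects since the previous visit". Also, "All AEs will be recorded appropriately, whether or not considered related to the investigational product". The sources named are the patient's own reports, observation by the research team, "as well as AEs reported in response to a direct question". Among the items described for each event is "Discovery (i.e., spontaneous or solicited").
- **Table 1.** Adverse events are collected at baseline and at weeks 2, 4 and 8, with no filter on discovery.
- **Statistical analysis plan.** The one analysis set, the full analysis set, requires at least one dose and at least one valid post-baseline primary-outcome assessment. Neither the primary model nor the list of secondary analyses includes adverse events. The nearest thing to a tolerability comparison is "Withdrawal rates will be compared between placebo- and vortioxetine-randomized participants at week 8".

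**The concern.** The listed outcome uses one of the two labels by which the protocol sorts its own events. An analyst who follows the list can select the spontaneous events from the discovery field and report those alone, while one who follows the recording sections would report everything. Both could claim to be following the protocol, and nothing in the statistical section decides between them. The choice could therefore be made after the data have been seen.

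The opening background text says that no treatment has yet been identified as safe and effective in this condition, so the safety result carries weight. The Side effects section gives gastrointestinal events at 21-32%, with incidence highest in the first week, and sexual dysfunction at 14-34%. The first kind can arise and settle before the week 2 visit, and the second may plausibly not be volunteered. Both are the kind of event that a direct question is meant to bring out.

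**Working it through.** There is no stated figure to reproduce, so the check is a comparison of the text.

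1. **Does spontaneous have a narrower meaning here than recorded?** Yes. Recordings of Adverse Events sets answers to a direct question apart from spontaneous reports, and the discovery field repeats the split as spontaneous or solicited. An event elicited by the visit question is solicited in the protocol's own terms, so it falls outside the outcome as worded.

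2. **Could spontaneous loosely cover answers to an open, non-leading question?** Not in this protocol. Its example of a direct question is itself an open one about health problems or side effects since the last visit.

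3. **Where do staff-observed events belong?** This is unclear. The recording sentence groups them with the patient's spontaneous reports before it adds the direct-question events. The discovery field has two values and assigns observed events to neither.

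4. **Does any analysis rule settle the scope?** No. The one rule given for analytic purposes, under Assessment of Causality, concerns the relation to study drug and sets no filter on discovery. The Statistical analysis plan has no adverse-event table, no between-arm adverse-event comparison and no safety set.

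5. **Would the existing analysis set serve for safety?** Not reliably. Table 1 schedules the DSST at baseline, week 2 and week 8, so week 2 is the first planned post-baseline assessment. A participant who took study drug and stopped before then could lack a valid one and drop out of the full analysis set. This is possible rather than certain, because Withdrawal Procedures and Next Steps has the Table 1 data collected up to and including withdrawal, which may yield an early DSST. The withdrawal-rate comparison is worded by randomised arm, so it may still count such a participant, but it would not describe the event.

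6. **Can the size be computed?** No. The documents give no event rates by mode of discovery, no placebo rates and no planned adverse-event test. Only the direction can be stated. Suppose a fraction f of affected participants volunteer the event, equal in both arms (an assumption), and the true proportions are p1 on drug and p0 on placebo. The spontaneous-only proportions are then f × p1 and f × p0. Their difference is f × (p1 − p0), which is smaller than p1 − p0 in absolute size when f < 1 and the two proportions differ. Their ratio is p1/p0, unchanged. If f differs between arms, the ratio changes as well.

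**The case against.** The best defence is that the outcome list is shorthand and the detailed sections govern. Those sections record all adverse events, Table 1 has no filter, and the outcome line does not say that solicited events are excluded. Serious adverse event reporting, the listed reasons for early termination and the rules for clinically significant laboratory changes do not depend on how an event was discovered. Every event stays in the database.

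Much of this stands. A reader might infer that the trial will count spontaneous reports only, and that its safety comparison will omit the rest. The documents do not support that: the outcome line contains no such restriction, and no adverse-event comparison is specified from which events could be omitted. Nor do they support the inference that staff-observed events would be lost, since the recording sentence places them beside spontaneous reports.

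A reader might also want a figure for the loss of power to detect a named side effect. That would need an assumed placebo rate and assumed volunteering fractions, and would describe a test that the plan does not contain.

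The defence does not remove the disagreement. An outcome list is where a reader looks to learn what will be reported, and here it uses a term that the recording section defines more narrowly than the data collected. The statistical section, which could have settled the matter, is silent.

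**Conclusion.** The point holds as a conflict over the scope of the adverse-event outcome. Followed as written, the outcome list leaves solicited events out; the recording sections include them; the position of staff-observed events is unclear. The statistical section adds a second gap: no adverse-event summary, and a single analysis set that could exclude participants who stop before week 2.

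The size cannot be derived. The conclusion rests on taking spontaneous and solicited in the sense in which the protocol itself contrasts them. It does not rest on any assumed event rate. Sample size, significance level, power and the primary efficacy analysis are unaffected. The correction is worth making before unblinding, because until then the content of the safety result is open to choice.

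**What to change.** - **Outcomes, Safety outcomes.** Define the outcome as all adverse events recorded under Safety Assessments and Recordings of Adverse Events, whatever their mode of discovery. Keep discovery mode as a descriptor and state how staff-observed events are coded. Those two sections start the recording window at different points (signature of consent, and baseline), so the definition should also state the window.
- **Statistical analysis plan.** Add a safety set of all participants who took at least one dose, with no requirement for a post-baseline DSST. In that set, summarise by arm the number and proportion of participants with any adverse event, any serious adverse event and any adverse event leading to withdrawal. A breakdown by discovery mode is optional.

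The cost is one reworded outcome line, a short definition and one table, using data already collected. The only downside is that reported adverse-event rates will be higher than under a spontaneous-only count.
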